10.0 MEASUREMENT OF EFFECT

10.1 The primary endpoint of this dose finding study is safety and to assess the toxicity associated with escalating doses of SBRT. Secondary endpoints include disease response, as measured by clinical examination and the accompanying imaging studies obtained at 3, 6, and 12 months post SBRT. Response will be measured according to standard RECIST criteria as follows:

Response	Evaluation of Target Lesions
Complete Response (CR)	Disappearance of all targeted lesion(s), or significant shrinkage of disease and metabolic response with SUV <4. Residual tissue fullness, asymmetry or fibrosis that continues to improve on serial CT imaging after an initial decline (>50%) in SUV will be considered treatment effect.
Partial Response (PR)	At least a 30% decrease in the sum of diameters of targeted lesion(s), taking as reference the baseline sum of diameters, and or a >50% decrease in tumor SUV.
Progressive Disease (PD)	At least a 20% increase in the sum of diameters of targeted lesions, taking as reference the smallest sum

	on study (this includes the baseline sum if that is the smallest on study). In addition to the relative increase of 20%, the sum must also demonstrate an absolute increase of at least 5 mm.
Stable Disease (SD)	Neither sufficient shrinkage to qualify for PR nor sufficient increase to qualify for PD, taking as reference the smallest sum diameters while on study.

11.0 DATA REPORTING/REGULATORY CONSIDERATIONS

Adverse event lists, guidelines, and instructions for AE reporting can be found in Section 8.0 (Adverse Events: List and Reporting Requirements).

11.1 Data Reporting

The OnCore Database will be utilized, as required by the Case Comprehensive Cancer Center, to provide data collection for both accrual entry and trial data management. OnCore is a Clinical Trials Management System housed on secure servers maintained at Case Western Reserve University. OnCore properly used is compliant with Title 21 CFR Part 11. Access to data through OnCore is restricted by user accounts and assigned roles. Once logged into the OnCore system with a user ID and password, OnCore defines roles for each user which limits access to appropriate data. User information and password can be obtained by contacting the OnCore Administrator at [contact].

OnCore is designed with the capability for study setup, activation, tracking, reporting, data monitoring and review, and eligibility verification. This study will utilize electronic Case Report Form completion in the OnCore database. A calendar of events and required forms are available in OnCore.

11.2 Regulatory Considerations

The study will be conducted in compliance with ICH guidelines and with all applicable federal (including 21 CFR parts 56 & 50), state or local laws.

11.2.1 Written Informed consent

Provision of written informed consent must be obtained prior to any study-related procedures. The Principal Investigator or Co investigators will ensure that the subject is given full and adequate oral and written information about the nature, purpose, possible risks and benefits of the study as well as the subject's financial responsibility. Subjects must also be notified that they are free to discontinue from the study at any time. The subject should be given the opportunity to ask questions and allowed time to consider the information provided.

The original, signed written Informed Consent Form must be kept with the Research Chart in conformance with the institution's standard operating procedures. A copy of the signed written Informed Consent Form must be given to the subject.

11.2.2 Subject Data Protection

In accordance with the Health Information Portability and Accountability Act (HIPAA), a subject must sign an authorization to release medical information to the sponsor and/or allow the sponsor, a regulatory authority, or Institutional Review Board access to subject's medical information that includes all hospital records relevant to the study, including subjects' medical history.

11.2.3 Retention of records

The Principal Investigator of The Case Comprehensive Cancer Center supervises the retention of all documentation of adverse events, records of study drug receipt and dispensation, and all IRB correspondence for as long as needed to comply with national and international regulations. No records will be destroyed until the Principal Investigator confirms destruction is permitted.

11.2.4 Audits and inspections

Authorized representatives of the sponsor, a regulatory authority, an Independent Ethics Committee (IEC) or an Institutional Review Board (IRB) may visit the Center to perform audits or inspections, including source data verification. The purpose of an audit or inspection is to systematically and independently examine all study-related activities and documents to determine whether these activities were conducted, and data were recorded, analysed, and accurately reported according to the protocol, Good Clinical Practice (GCP), guidelines of the International Conference on Harmonization (ICH), and any applicable regulatory requirements.

11.2.5 Data Safety and Monitoring Plan

This protocol will adhere to the policies of the Case Comprehensive Cancer Center Data and Safety Monitoring Plan in accordance with NCI regulations.

12.0 STATISTICAL CONSIDERATIONS

The main endpoint of this dose finding study is safety and to identify the maximum tolerated dose of SBRT in this patient population. Dose escalation studies typically involve a “3+3” design. However, as SBRT is a powerful treatment tool, and toxicities can be delayed, we erred on the conservative side and doubled our dose level population. As such, we have planned for accrual of 6 patients to each dose level. If sufficient DLTs are not seen in the third dose level (45Gy in 5 fraction), then an additional 6 patients will be accrued to this dose level to provide more robust safety information on this dose, which would become the recommended dose for future study. We also performed probability analysis using binomial distribution analysis to calculate the probability of escalating to each dose level, as demonstrated in the following table:

p of	Dose 1- p of <=1 DLT in	Dose 1- p of 2 DLT in 1st	Dose 1- p of <=1 DLT in	p for Next
------	-------------------------	---------------------------	-------------------------	------------

DLT	1st 6 pts	6 pts	2nd 6 pts	Dose
0.15	0.78	0.18	0.78	0.91
0.2	0.66	0.25	0.66	0.82
0.25	0.53	0.30	0.53	0.69
0.3	0.42	0.32	0.42	0.56
0.4	0.23	0.31	0.23	0.31

For our secondary endpoints, we will also use Kaplan-Meier estimates to plot overall survival and local progression free survival. We will conduct trend tests to investigate the relationship between SBRT dose and response. Non-parametric methods, including but not limited to the Mann-Whitney test and Fisher's exact test, will be used to analyze patient, tumor and treatment related factors associated with SBRT related morbidity, including DLTs as well as grade 3 acute and late events. We will use repeated ANOVA measures to analyze the quality of life data.

REFERENCES

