2.0 OBJECTIVES

2.1 Primary Objective: To explore the maximum tolerated dose of head and neck SBRT in a high risk patient population ineligible for standard chemoradiotherapy. Two dose levels will be used 40Gy, 45Gy all in 5 fractions.

2.2 Secondary Objectives:

- 2.2.1 Assess profiles of SBRT toxicity and examine patient (including co-morbidities), tumor and treatment related factors that are associated with SBRT related toxicity
- 2.2.2 identify any dose volume parameters that are associated with SBRT related toxicity
- 2.2.3 explore potential dose response relationships between higher SBRT dosing and radiographic response
- 2.2.4 assess impact of SBRT on patients quality of life

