3.2 Patient Enrollment

We plan on enrolling a maximum of 18 patients to this study. This relies on the traditional 3+3 approach used in many chemotherapy phase I studies, but we have doubled the number in each arm to ensure we capture potential toxicities which can be delayed.

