4.1 Inclusion Criteria

Patients must meet all of the following inclusion criteria to be eligible for enrollment:

_____ 4.1.1 The patient must have squamous cell carcinoma, adenocarcinoma or malignant salivary gland cancer (e.g. acinic cell, adenoid cystic, mucoepidermoid, salivary duct carcinoma) proven by histologic diagnosis. Both mucosal and cutaneous cancers are eligible.

_____ 4.1.2 The patient must have clinical stage T1-4, N0-3, M0-1, stage II-IVC carcinoma as per the 7th edition of the AJCC staging manual. Patients with T1N0M0 will be ineligible. Patients with metastatic disease with a limited metastatic burden are eligible if obtaining local control is determined by their treating oncologist to be an important therapeutic goal.

_____ 4.1.3 The patient must have imaging documenting a primary tumor, or involved lymph node, $\geq 2.5\text{cm}$ in greatest dimension.

_____ 4.1.4 PET/CT is required for all patients, unless contraindicated. This may be acquired prior to study entry or after enrollment prior to SBRT planning.

_____ 4.1.5 The patient must have a history and physical documented within four weeks of registration and be deemed by a medical oncologist to be ineligible for standard continuous course chemoradiotherapy with Cisplatin, or refuse treatment with Cisplatin.

_____ 4.1.6 Performance status - Karnofsky PS ≥ 40

_____ 4.1.7 Age ≥ 18 years.

- _____ 4.1.8 Female patients can not be of childbearing age, or if they are, must have a negative pregnancy test prior to enrollment and be willing to use contraceptives during treatment and continue for 6 additional months.
- _____ 4.1.9 Patients must have the ability to understand and the willingness to sign a written informed consent document.

4.2 **Exclusion Criteria**

The presence of any of the following will exclude a patient from study enrollment.

- _____ 4.2.1 Patients with T1N0M0 stage I disease.
- _____ 4.2.2 Patients who are receiving any other investigational agents.
- _____ 4.2.3 Patients with non-malignant histology.
- _____ 4.2.4 Patients with life expectancy <6 months.
- _____ 4.2.5 Patients who cannot lie flat for 20 minutes.
- _____ 4.2.6 Patients with prior history of head and neck radiotherapy (>40Gy) with significant areas of anticipated overlap

4.3 **Inclusion of Women and Minorities**

Both men and women and members of all races and ethnic groups are eligible for this trial.

5.0 **Registration**

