6.4 Duration of Follow Up

Patients will be followed for toxicity for 1 year after treatment has been discontinued or until death, whichever occurs first. Following completion of this period of follow-up on-study patients will then be followed per standard of care as detailed below.

The clinical course of each event will be followed until resolution, stabilization, or until it has been determined that the study treatment or participation is not the cause. Serious adverse events that are still ongoing at the end of the study period will necessitate follow-up to determine the final outcome.

Patients will be followed for one year after SBRT. All patients will be seen at 0.5, 3, 6, 9, 12 months after SBRT. At the three month visit, a post-SBRT PET/CT will be obtained to assess for disease response. CT of the neck and chest (preferably with contrast barring allergies or renal insufficiency) will be obtained at the 6 and 12 month visits. At each visit, patients will be assessed for Head and Neck toxicity using the Common Terminology Criteria for Adverse Events (CTCAE) version 4.0. While no other toxicities are expected, any additional toxicity should also be scored by CTCAE version 4.0. In addition they will complete the FACT-H&N questionnaire (validated questionnaires to assess treatment related quality of life). When study follow-up is completed at 12 months, the patient will transition to standard follow-up off protocol with physician visits and head and neck exam every 3 months for year 2, every 4 months for year 3, every 6 months for year 4 and annually thereafter.

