9.0 STUDY PARAMETERS AND CALENDAR

9.1 Study Parameters

9.1.1 Screening Evaluation

Patients will complete the FACT H&N quality of life questionnaires at baseline.

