9.2 Calendar

Assessment	Months Since Treatment					
	Baseline	0 Post Treatment (Last OTR Visit)	0.5 (1-3wks)	3	9	6, 12
Informed Consent	X					
Medical History	X					
Vitals ¹	X	X	X	X	X	X
Physical Exam ²	X	X	X	X	X	X
PET/CT ³	X			X		
CT neck and chest ⁴						X
FACT-H&N survey	X		X	X	X	X
CTCAE Toxicity Assessment		X	X	X	X	X

¹ Height not required

² Focused head and neck exam at each visit with optional pharyngolaryngoscopy

³ An additional PET/CT may be done after the 3 month time point to help clarify the etiology of abnormalities that are found clinically or radiographically to suggest potential recurrence/progression

⁴ With contrast unless contraindicated

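### Quality of life is to be analysed by an unspecified repeated-measures ANOVA with no rule for deaths or missing forms; in its standard form over all six assessments it would discard every patient without a complete set.

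*Combined protocol and SAP*

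**What the plan says.** Secondary objective 2.2.4 is to "assess impact of SBRT on patients quality of life". The instrument is FACT-H&N, given six times:

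- Section 9.1.1 sets the baseline form: "Patients will complete the FACT H&N quality of life questionnaires at baseline".
- Section 6.4 lists visits at 0.5, 3, 6, 9 and 12 months and adds: "In addition they will complete the FACT-H&N questionnaire".
- The calendar in section 9.2 agrees. Its "FACT-H&N survey" row is marked at baseline and at those five visits, and not at the end-of-treatment visit.

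The whole analysis plan is one sentence in section 12.0: "We will use repeated ANOVA measures to analyze the quality of life data". It does not say which form of the method is meant, which score or visits enter it, which patients are included, or what happens after a death or a missed form. No other section fills these gaps.

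The protocol expects that some patients may die during the year. Section 6.4 states: "Patients will be followed for toxicity for 1 year after treatment has been discontinued or until death, whichever occurs first". Section 4.1 admits Karnofsky scores down to 40 and limited metastatic disease. On prognosis, section 4.2.4 excludes only "Patients with life expectancy <6 months". On size, section 3.2 states: "We plan on enrolling a maximum of 18 patients to this study".

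**The concern.** Repeated-measures ANOVA in its standard form needs a complete row for each patient. Over six assessments, a patient who dies in month 8, or who misses only the 9-month form, leaves the analysis altogether. The scores that patient gave at 0.5 and 3 months, soon after SBRT, leave with them. A patient with an expected survival of 7 to 11 months meets the entry criteria but would not be expected to supply all six forms.

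Two things are at stake. The first is precision, in a trial of at most 18 patients. The second is whom the result describes: objective 2.2.4 would be answered only in 12-month survivors with full attendance. If sicker patients score lower and are lost more often, the average level reported would be too high.

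**Working it through.** The plan gives no sample size, attrition or completion figure for quality of life, so there is none to reproduce. What follows is an illustration of scale.

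**Inputs**
- N = 18, the cap in section 3.2.
- One-year survival S = 0.38 and 0.70, the lowest and highest values in the re-irradiation table of section 1.3. This is a proxy, because the same section says survival may be longer in the present population. S = 0.85 is therefore added as an assumption.
- Completion per post-SBRT visit while alive, c = 1.00 or 0.90. This is assumed, as the documents give no rate. Baseline is taken as always obtained.

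**Complete cases** = N × S × q, where q is the chance that a 12-month survivor returns all five post-SBRT forms.
- No missed forms: q = 1.
- c = 0.90, misses independent across visits: q = 0.90^5 = 0.590.
- c = 0.90, misses clustered within patients (beta-binomial, correlation 0.5): q = 0.9/1 × 1.9/2 × 2.9/3 × 3.9/4 × 4.9/5 = 0.790.

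| Complete cases of 18 (share lost) | S = 0.38 | S = 0.70 | S = 0.85 |
|---|---|---|---|
| Deaths only | 6.8 (62%) | 12.6 (30%) | 15.3 (15%) |
| c = 0.90, independent | 4.0 (78%) | 7.4 (59%) | 9.0 (50%) |
| c = 0.90, clustered | 5.4 (70%) | about 10 (45%) | 12.1 (33%) |

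If accrual stops at 12 (6 at each of two levels), deaths alone leave 12 × 0.38 = 4.6 to 12 × 0.70 = 8.4.

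**Early forms left out.** Assume a constant hazard, S(t) = S^(t/12). Forms collected at 0.5 and 3 months = 18 × c × [S(0.5) + S(3)]. Forms used = 2 × complete cases.
- c = 1: collected 31.4, 34.2 and 35.2 for the three values of S; used 13.7, 25.2 and 30.6; left out 56%, 26% and 13%.
- c = 0.90: collected 28.3, 30.8 and 31.6. Left out 71%, 52% and 43% if misses are independent, and 62%, 35% and 24% if clustered.

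**Mechanism.** In simulated data for 18 patients and 6 visits, with 8 patients missing the last two, 108 − 16 = 92 observations remain. A standard repeated-measures ANOVA routine rejected the data as unbalanced. After listwise deletion it ran on 10 patients, with error degrees of freedom (10 − 1) × (6 − 1) = 45. A linear mixed model used all 18 patients and all 92 observations.

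**Direction of bias.** At a visit where both groups have been observed, let p be the share of observed patients later excluded. The complete-case mean differs from the mean of all observed patients by p × (completers' mean − excluded patients' mean). The identity holds separately for levels and for changes from baseline.
- Level: at baseline with deaths only, p = 0.62, 0.30 or 0.15. Each point by which excluded patients score lower raises the reported baseline mean by that fraction of a point.
- Change: an excluded patient takes their own low baseline with them. If both groups change equally, the difference is p × 0 = 0. Early change looks too favourable only if excluded patients also worsen more.

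**The case against.** The strongest reply is that the plan does not prescribe this loss. The sentence in section 12.0 names no complete-case rule, and its loose wording does not exclude a mixed model or a subset of visits. An additive patient-plus-visit ANOVA accepts incomplete rows, and on the simulated pattern above it too used all 18 patients and 92 observations. This stands. A reader might infer that the protocol restricts quality of life to survivors, but the documents support only the conditional statement. The gap remains, because two permissible readings give very different analysis sets and the choice would be made after the data are seen.

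A reader might also infer that the reported effect of SBRT would probably look too favourable. That does not follow from sicker patients scoring lower. It needs the further condition that lost patients worsen more, which is plausible but which nothing in the documents establishes.

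The size is also uncertain. A range of 13% to 71% of early forms shows that the documents do not fix it, since completion is assumed and survival is borrowed from another population. Lastly, this is one secondary objective of a phase I trial, with no hypothesis or threshold attached. CTCAE captures toxicity separately, and observed scores could still be tabulated, though the plan does not ask for it. These points limit the importance of the gap but do not remove it.

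**Conclusion.** The concern holds in a bounded form. The plan names one method for data that are likely to be incomplete, and gives no rule for deaths or missing forms. If the method is run in its standard form over all six assessments, deaths alone would leave about 7 to 13 of 18 patients at 38-70% one-year survival and about 15 at 85%. With 90% completion per visit, about 4 to 10 would remain at 38-70% survival and 9 to 12 at 85%, depending on whether missed forms cluster. With 85% survival and full completion the loss is modest.

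The firm consequence is lost precision. Average levels would be too high if sicker patients score lower and drop out more; a favourable bias in change from baseline needs the extra condition above. The figures rest on a possibly pessimistic survival proxy and assumed completion rates. Dose escalation and the primary endpoint are unaffected. The change is worth making because it is cheap and uses data already planned.

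**What to change.** Replace the sentence in section 12.0 with:

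> FACT-H&N total score will be analysed with a linear mixed model for repeated measures using all available assessments (visit as a categorical effect including baseline, patient random intercept, dose levels pooled), with Kenward-Roger small-sample degrees of freedom. Mean changes from baseline with 95% CIs will be reported by visit. Observed means among patients alive at each visit, with the numbers alive and the numbers completing the form, will be reported alongside.

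Dose levels are pooled, and no summaries by dose level or time of death are asked for, because each such group would hold only a handful of patients.

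The cost is a short rewording and one descriptive table, with the same forms and visits. The model assumes data are missing at random and implicitly extrapolates a patient's course after death, so its estimates should not be described as quality of life while alive. The observed means serve that purpose, though they describe a changing group from visit to visit. With at most 18 patients, all estimates stay imprecise.

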APPENDIX A: FACT-Head and Neck QOL Questionnaire

Below is a list of statements that other people with your illness have said are important. **Please circle or mark one number per line to indicate your response as it applies to the past 7 days.**

PHYSICAL WELL-BEING		Not at all	A little bit	Some-what	Quite a bit	Very much
GP1	I have a lack of energy.....	0	1	2	3	4
GP2	I have nausea	0	1	2	3	4
GP3	Because of my physical condition, I have trouble meeting the needs of my family	0	1	2	3	4
GP4	I have pain	0	1	2	3	4
GP5	I am bothered by side effects of treatment	0	1	2	3	4
GP6	I feel ill	0	1	2	3	4
GP7	I am forced to spend time in bed	0	1	2	3	4
SOCIAL/FAMILY WELL-BEING		Not at all	A little bit	Some-what	Quite a bit	Very much
GS1	I feel close to my friends	0	1	2	3	4
GS2	I get emotional support from my family	0	1	2	3	4
GS3	I get support from my friends.....	0	1	2	3	4
GS4	My family has accepted my illness	0	1	2	3	4
GS5	I am satisfied with family communication about my illness.....	0	1	2	3	4
GS6	I feel close to my partner (or the person who is my main support).....	0	1	2	3	4
Q1	Regardless of your current level of sexual activity, please answer the following question. If you prefer not to answer it, please mark this box  and go to the next section.					

GS7

I am satisfied with my sex life..... 0 1 2 3 4

Please circle or mark one number per line to indicate your response as it applies to the past 7 days.

EMOTIONAL WELL-BEING

		Not at all	A little bit	Some- what	Quite a bit	Very much
GE1	I feel sad	0	1	2	3	4
GE2	I am satisfied with how I am coping with my illness	0	1	2	3	4
GE3	I am losing hope in the fight against my illness	0	1	2	3	4
GE4	I feel nervous	0	1	2	3	4
GE5	I worry about dying	0	1	2	3	4
GE6	I worry that my condition will get worse	0	1	2	3	4

FUNCTIONAL WELL-BEING

		Not at all	A little bit	Some- what	Quite a bit	Very much
GF1	I am able to work (include work at home)	0	1	2	3	4
GF2	My work (include work at home) is fulfilling.....	0	1	2	3	4
GF3	I am able to enjoy life.....	0	1	2	3	4
GF4	I have accepted my illness.....	0	1	2	3	4
GF5	I am sleeping well.....	0	1	2	3	4
GF6	I am enjoying the things I usually do for fun	0	1	2	3	4
GF7	I am content with the quality of my life right now.....	0	1	2	3	4

Please circle or mark one number per line to indicate your response as it applies to the past 7 days.

ADDITIONAL CONCERNS		Not at all	A little bit	Some-what	Quite a bit	Very much
H&N1	I am able to eat the foods that I like	0	1	2	3	4
H&N2	My mouth is dry	0	1	2	3	4
H&N3	I have trouble breathing.....	0	1	2	3	4
H&N4	My voice has its usual quality and strength.....	0	1	2	3	4
H&N5	I am able to eat as much food as I want	0	1	2	3	4
H&N6	I am unhappy with how my face and neck look.....	0	1	2	3	4
H&N7	I can swallow naturally and easily.....	0	1	2	3	4
H&N8	I smoke cigarettes or other tobacco products	0	1	2	3	4
H&N9	I drink alcohol (e.g. beer, wine, etc.).....	0	1	2	3	4
H&N ₁₀	I am able to communicate with others.....	0	1	2	3	4
H&N ₁₁	I can eat solid foods.....	0	1	2	3	4
H&N ₁₂	I have pain in my mouth, throat or neck.....	0	1	2	3	4

